## 8.2 PLACEBO

### 8.2.1 Overview – Prescribing Information

#### **Test Product**

Substance:	Placebo
Strength:	0 mg
Dosing frequency	Twice daily
Mode of administration:	Oral tablets
Manufacturer:	Emerson Resources

### 8.2.2 Packaging and Labeling Information

The placebo will be packaged and labeled in accordance with all applicable regulatory requirements and Good Manufacturing Practice guidelines.

Placebo will be supplied in high-density polyethylene bottles.

Study medications (placebo) will be shipped and stored under controlled conditions according to the storage requirements.

Refer to the pharmacy manual for full details for packaging, labeling, and shipment of the placebo.

The funder, Aclaris, or designee will supply the placebo medications.

### 8.2.3 Preparation/Mixing Instructions

Placebo will be produced as a solid, pre-formulated, rapidly disintegrating tablet. No additional patient preparation or mixing will be necessary for the patient prior to taking it.

### 8.2.4 Drug Storage and Stability

The investigator (or designee) is responsible for the safe and proper storage of the placebo at the site. The placebo will be stored under controlled conditions according to the storage requirements described on the label(s). The placebo should be stored at 15°C to 25°C (59°F to 77°F), away from heat moisture and direct light. The investigator (or designee) will instruct the patients to store the placebo medication in accordance to the instructions on the label(s).

In case of temperature excursion, the investigation team will be notified and noted in patient record. No change or pill replacement are planned.

### 8.2.5 Acquisition and Accountability

The placebo must not be used for any purpose other than that defined in this protocol. All supplies of placebo will be accounted for in accordance with Good Clinical Practice (GCP).

The pharmacist or (designee) should maintain accurate records of all study placebo supplies received during the study. These records should include the dates and amounts of study placebo that were received at the site, dispensed, and destroyed or returned to the sponsor (or designee). The records should include dates, quantities, batch/serial numbers, expiration dates (if applicable), and the unique code numbers assigned to the study medication and study patients. If errors or damage in the study placebo shipments occur, the investigator should contact the sponsor (or its designee) immediately. Copies of the study placebo accountability records will be provided by each investigator for inclusion in the trial master file (TMF). The study monitor will periodically check the supplies of study placebo held by the investigator or pharmacist to verify accountability of the study placebo used.

The investigator (or designee) will explain the correct use of the blinded study placebo to each patient and will check that each patient is following the instructions properly. The investigator (or designee) will provide the blinded study placebo to the investigational pharmacy which will then be dispensed to the patient twice daily. The patient will self-administer the placebo twice daily in this study, according to the procedures described in this study protocol.

A record of the number of tablets of placebo dispensed to and taken by each patient will be maintained and reconciled with study placebo and compliance records. The study placebo start and stop dates, including dates for study placebo delays and/or dose reductions, will also be recorded in the eCRF. After the end of the study, all unused study placebo and all placebo containers should be destroyed at the study center or returned to the sponsor (or designee) for destruction. In either instance, complete documentation will be returned to the sponsor.

## 9 TREATMENT PLAN

The study drug / placebo will be administered within a 14-day cycle. Treatment will be administered to patients while they are hospitalized and will continue their 14-day course of medication as an inpatient. If the patient is discharged alive before treatment is completed, the patient will discontinue drug / placebo but remain on study.

Reported adverse events and potential risks are described in Adverse Events section.

### 9.1 Treatment Regimen

#### 9.1.1 Treatment Plan

##### Drug Treatment Schedule

Pre-medications	None
Dose of ATI-450 or Placebo	1 tablet – placebo or 50 mg (as determined from Phase I study) (100 mg total per day).
Route	Oral tablet
Duration of Administration	Up to 14 days while inpatient or if appropriate for discharge home then drug or placebo will be discontinued on last day of being in the hospital
Schedule	Pill will be taken twice daily preferably spaced $12 \pm 1$ hours apart

#### 9.1.2 PARTICIPANT ACCESS TO STUDY AGENT AT STUDY CLOSURE

Participants will not have access to the study agent at study closure.

#### 9.1.3 DOSE ADJUSTMENTS/MODIFICATIONS/DELAYS

Participants who experience a grade  $\geq 3$  toxicity will be evaluated by the medical monitor and study co-PI's, and the case will be forwarded within 24 hours to the KUMC DSMB team to evaluate whether toxicity is attributable to study drug. The DSMB will recommend whether or not patient should be removed from study treatment. There is no planned dose adjustment. Should the patient develop a fungal or bacterial infection while being treated with ATI-450, then the patient will be evaluated as above but will be taken off drug prior to any decision by the DSMB.

## 10 STUDY PROCEDURES AND SCHEDULE

### 10.1 Screening/Enrollment/Baseline

Because this is an acute illness, many of the tests required at screening which are performed as part of standard of care within day -2 thru day 0 prior to signing consent will be allowed in this study. Because additional screening labs may be necessary to assess for eligibility after informed consent is obtained, labs from the time of signing informed consent and prior to randomization will be allowed to further assess eligibility in this study. The total

“screening period” will be 96 hours (day -2 through day of enrollment with an additional 2 days after enrollment so that additional screening labs and tests can be performed and resulted). . All resulted screening labs will be reviewed by the investigator. The most recent available resulted labs will be used by the investigator to ensure I/E criteria are met prior to enrollment/randomization.

The following are study procedures. Daily monitoring and care will occur as standard practice.

**NOTE: This trial will consist of only one 14 day treatment cycle**

**Day -2 up to screening day 2**

- Informed Consent
- Eligibility review
- COVID-19 and other medical history including time since onset of symptoms and reason for hospital admission
- Demographics - including date of birth, gender, race, ethnicity, and zip code
- Review participant eligibility criteria to ensure participant qualification for study entry
- HIV and Hepatitis history
- Full Physical exam
- Vital signs, weight and height
- Prior and concomitant medications
- Assess for ARDS
- 24 hour COVID-19 PCR testing§
- Blood gases (if historic values are available)\*
- 12-Lead ECG\*¥
- CBC with differential\*
- CMP\*
- C-Reactive Protein\*
- Ferritin\*
- D-dimer\*
- LDH\*
- Pro-calcitonin\*
- Serum pregnancy test\*

§ For subsites, one can forego another COVID-19 PCR test if that test was performed at the same hospital facility within the screening period. Day 14 (or discharge < day 14) and day 28 COVID-19 PCR tests should be performed using the same assay by the same institution as the Day 0 COVID-19 PCR test for pre-post comparison.

\*Historic Lab Values can be used if test performed Day -2 through Day 0

¥ INR alone will be acceptable if PT value is not reported

#### 10.1.1 Procedures During Treatment

**Hospital Day 1 (Baseline)**

- Limited physical exam
- Vital signs and SpO2 and FiO2
- Urine Output

- Adverse event assessment
- Prior and concomitant medications
- Assess for ARDS
- WHO COVID-19 Ordinal Scale
- Drug Accountability
- CBC with differential
- PT, INR€
- PTT
- CMP
- Mg
- GGT
- C-Reactive Protein
- Ferritin
- D-dimer
- LDH
- Phosphate
- Troponin-I
- Cystatin C
- Pro-calcitonin
- Creatine Kinase
- Urinalysis ¥
- Documentation of proning
- Research Blood Draw Tube #1-4 (prior to morning study drug dose): see chart below for site specific requirements
- Research Blood Draw Tube #5 (hour prior to morning study drug dose): see chart below for site specific requirements (KUMC only)
- Research buccal mucosa tissue brushing (DNA collection) (provide patient Appendix C instructions) Research saliva collection
- Research Urine Collection (prior to morning study drug dose): see chart below for site specific requirements ¥

¥ Urine collection and ECG before drug administration is preferred. However, tests collected after morning specimen collection and/or after drug administration will be considered acceptable.

€ INR alone will be acceptable if PT value is not reported

**Research Specimen Collection Guide\* ♦**

Collection Tube	Non KUMC Sites	KUMC Only
Research Tube #1 (red top/no additive)	Serum	Serum
Research Tube #2 (lavender top/EDTA)	Plasma + Buffy Coat	Plasma; PBMC pooled (RNA, protein, immunophenotyping, neutrophil studies)
Research Tube #3 (lavender top/EDTA)	Plasma + Buffy Coat	
Research Tube #4 (lavender top/EDTA)	Plasma	
Research Tube #5 (lavender top/EDTA)	Not Applicable	PBMC (rapid prep) (scRNASeq, RNA, protein)
Research Buccal Mucosa Swab	Buccal Swab (DNA, microbiome)	Buccal Swab (DNA, microbiome)
Research Saliva Collection	Not Applicable	Saliva collection
Research Urine Collection	Urine Supernatant	Urine Supernatant

\*See Specimen Processing Protocol for processing and shipment instructions

♦ If research specimens become hemolyzed, specimens are to be redrawn (pre- or post-dose)

**After research labs have been drawn**

- Morning and evening (BID) administration of study medication

**Hospital DAY 2 –**

- **OPTIONAL EKG - for patients previously on hydroxychloroquine discontinued at randomization; 24 hours ± 2 hour after initiation of drug**
- Morning and evening (BID) administration of study medication
- Vital signs and SpO2 and FiO2
- Urine Output
- Adverse event assessment
- Assess for stoppage criteria
- Drug Accountability

**Hospital Day 3 (48 hours post initiating study medication)**

- Limited physical exam
- Vital Signs and SpO2 and FiO2
- Urine Output

- Adverse event assessment
- Assess for stoppage criteria
- Concomitant medications
- Assess for ARDS
- Drug Accountability
- WHO COVID-19 Ordinal Scale
- CBC with differential
- PT, INR
- PTT
- CMP
- Mg
- GGT
- C-Reactive Protein
- Ferritin
- D-dimer
- LDH
- Phosphate
- Troponin-I
- Cystatin C
- Creatine Kinase
- 12 Lead ECG¥
- Documentation of proning
- Research Blood Draw Tube #1-4 (prior to morning study drug dose): see chart above for site specific requirements
- Research Blood Draw Tube #5 (prior to morning study drug dose): see chart above for site specific requirements (KUMC only)

**After all research have been drawn**

- Morning and evening (BID) administration of study medication

**Hospital Day 4-6**

- Morning and evening (BID) administration of study medication
- Assess for stoppage criteria
- Urine Output
- Adverse event assessment
- Assess for ARDS
- Drug Accountability

**Hospital Day 7 (or at discharge < day 7)**

- Limited physical exam
- Vital signs and SpO2 and FiO2
- Urine Output
- Adverse event assessment
- Assess for stoppage criteria
- Concomitant medications
- Assess for ARDS

- WHO COVID-19 Ordinal Scale
- Drug Accountability
- CBC with differential
- PT, INR
- PTT
- CMP
- Mg
- GGT
- C-Reactive Protein
- Ferritin
- D-dimer
- LDH
- Phosphate
- Troponin-I
- Cystatin C
- Creatine Kinase
- Urinalysis ¥
- Documentation of proning
- Research Blood Draw Tube #1-4 (prior to morning study drug dose): see chart above for site specific requirements
- Research Blood Draw Tube #5 (prior to morning study drug dose): see chart above for site specific requirements (KUMC only)
- Research buccal mucosa tissue brushing (DNA collection) (provide patient Appendix C instructions]
- Research saliva collection
- Research Urine Collection (prior to morning study drug dose): see chart above for site specific requirements ¥

**After research labs have been drawn**

- Morning and evening (BID) administration of study medication

**Hospital Day 8-13**

- Morning and evening (BID) administration of study medication
- Assess for stoppage criteria
- Urine Output
- Adverse event assessment
- Assess for ARDS
- Drug Accountability

**Day 14 - End of Treatment (discharge < day 14)**

- Limited physical exam to include vital signs and SpO2 and FiO2
- Urine Output
- Adverse event assessment
- Prior and concomitant medications
- Assess for ARDS
- WHO COVID-19 Ordinal Scale
- 24 hour COVID-19 PCR testing

- Drug Accountability
- 12 Lead ECG¥
- Survival Status
- CBC with differential
- PT, INR
- PTT
- CMP
- Mg
- GGT
- C-Reactive Protein
- Ferritin
- D-dimer
- LDH
- Phosphate
- Troponin-I
- Cystatin C
- Pro-calcitonin
- Creatine Kinase
- Urinalysis¥
- Documentation of proning
- Research Blood Draw Tube #1-4 (prior to morning study drug dose): see chart above for site specific requirements
- Research Blood Draw Tube #5 (prior to morning study drug dose): see chart above for site specific requirements (KUMC only)
- 
- Research saliva collection
- Research Urine Collection (prior to morning study drug dose): see chart above for site specific requirements¥

**After research labs have been drawn**

- Morning and evening (BID) administration of study medication
- Return any and all unused drug to pharmacy for accounting purposes

---

**10.1.2 Post-Treatment Follow-Up Visits****Day 28 Post Hospital Day 1 ( $\pm 3$  days)**

- Limited physical exam
- Vital signs and SpO2 and FiO2
- Adverse event assessment
- Prior and concomitant medications
- WHO COVID-19 Ordinal Scale
- 24 hour COVID-19 PCR testing
- Survival Status
- 12 Lead ECG¥
- CBC with differential
- PT, INR

- PTT
- CMP
- Mg
- GGT
- C-Reactive Protein
- Ferritin
- D-dimer
- LDH
- Phosphate
- Troponin-I
- Cystatin C
- Creatine Kinase
- Urine pregnancy
- Urinalysis
- Research Blood Draw Tube #1-4: see chart above for site specific requirements
- Research Blood Draw Tube #5: see chart above for site specific requirements (KUMC only)
- Research buccal mucosa tissue brushing (DNA collection) (provide patient Appendix C instructions]
- Research saliva collection
- Research Urine Collection: see chart above for site specific requirements

#### Safety Follow up

- **Day 45 Post Hospital Day 1 ( $\pm 3$  days)**
  - Vitals
  - Prior and concomitant medications
  - Follow-up adverse event status
  - Survival Status
  - Pregnancy status
  - CBC with differential
  - PT, INR
  - PTT
  - CMP
  - Mg
  - GGT
  - Creatine kinase
  - Troponin I
- **Day 60 Post Hospital Day 1 ( $\pm 3$  days)**
  - Phone call to follow up adverse event status
  - Survival Status

#### 10.2 Duration of Follow Up

Survival follow up assessments will be conducted 28, 45 and 60 days post hospital day 1 and all participants should complete these visits. Exceptions include death, lost to follow-up or the participant withdrawing consent for follow-up all of which should be documented in the participants medical record and EDC.

Discontinuation from treatment does not preclude the need to complete follow-up assessments.

### 10.2.1 Overall Survival Follow Up (OS-FU)

Participants will be followed for survival status until 60 days post hospital day 1 ( $\pm 3$  days) after end of treatment.

Assessment of survival may be completed by phone contact. Death information from public sources, (e.g. death registry, obituary listing, etc.), can also be used when it is available and verifiable.

Patients who are discharged from the hospital to home or another facility (i.e. rehab, SNF) before reaching day 14 of the study in the hospital will be contacted by a study team member by phone in order to collect patient vital status, oxygenation requirements (i.e. on room air, nasal canula, O2 flow rate), assess for any new adverse events or severe adverse events. Patients who cannot (or are unwilling) to return for day 28 or day 45 in-person follow-up visits will be contacted by phone call. Attempts will need to be made to try and collect study specimens and research labs at the appropriate times, if possible. Attempts will also be made to collect any outside records of laboratory data fulfilling study requirements.

### 10.3 Lost to Follow Up

Institution policy will be followed for participants considered lost to follow up.

## 10.4 Schedule of Events Table

	Day -2 up to screening day 2 	Hospital Day 1 	Hospital Day 2 	Hospital Day 3 	Hospital Days 4-6 	Hospital Day 7 	Hospital Days 8-13 	Day 14 (or D/C) 	F/U Day 28 	F/U Day 45 	F/U Day 60
Informed Consent	X										
Eligibility Review	X	X									
COVID-19, Medical History and Demographics	X										
Prior and Concomitant Medications	X	X		X		X		X	X	X	
Adverse Events		X	X	X	X	X	X	X	X	X	X
Height and Weight	X										
Full Physical Exam^8	X										
Limited Physical Exam^9		X		X		X		X	X		
HIV and Hepatitis History	X										
Vital Sign and O2 Usage	X	X		X		X		X	X	X	
Urine Output Monitor		X	X	X	X	X	X	X			
24-hour COVID-19 PCR test	X								X	X	
12-Lead ECG	X		X 	X 					X 	X	
CBC w/ Diff	X	X		X		X		X	X	X	
PT/INR		X		X		X		X	X	X	
PTT		X		X		X		X	X	X	
Complete Metabolic Panel	X	X		X		X		X	X	X	
Magnesium^6		X		X		X		X	X	X	
GGT		X		X		X		X	X	X	
C-Reactive Protein	X	X		X		X		X	X		
ferritin	X	X		X		X		X	X		
D-dimer	X	X		X		X		X	X		
LDH	X	X		X		X		X	X		
pro-calcitonin	X	X							X		
Phosphate		X				X		X	X		
Creatine Kinase		X		X		X		X	X	X	
Troponin-I		X		X		X		X	X	X	
Cystatin C		X				X		X	X		
Urinalysis		X				X		X	X		

	Day -2 up to screening day 2 	Hospital Day 1 	Hospital Day 2 	Hospital Day 3 	Hospital Days 4-6 	Hospital Day 7 	Hospital Days 8-13 	Day 14 (or D/C) 	F/U Day 28 	F/U Day 45 	F/U Day 60
Serum Pregnancy Test	X										
Urine Pregnancy Test									X		
Drug Dosing		X	X	X	X	X	X	X			
Drug Accountability		X	X	X	X	X	X	X			
Research Blood		X 		X 		X 		X 	X		
Research Urine Collection		X				X		X			
Research Buccal mucosa tissue brushing		X 				X 			X		
Research saliva collection		X 				X		X 	X		
ARDS Assessment	X	X	X	X	X	X	X	X			
WHO COVID-19 Ordinal Scale		X		X		X		X	X		
Stoppage Criteria Assessment			X	X	X	X	X				
Pregnancy status										X	X
Survival status								X	X	X	X

 Most recent value recorded in EMR^2 Recorded daily vital signs through hospitalization course (baseline thru day of discharge or Day 28). Record vital signs from 00:00 – 24:00 each Day. Vital signs to include: highest and lowest heart rate, highest and lowest respiratory rate, highest and lowest temperature, Highest SpO2 and FiO2 concurrent to highest SpO2, Lowest SpO2 and FiO2 concurrent to lowest SpO2, weight (if available), BP with highest systolic value, and BP with lowest systolic value. For patients previously on hydroxychloroquine discontinued at randomization; 24 hours ± 2 hour after initiation of drug Research lab tubes to be collected per respective site instructions (see table page 32). record daily while in the hospital drug accountability SOC lab values will be collected daily throughout hospitalization course (baseline thru day of discharge or Day 28 if available) SOC arterial blood gas values will be collected if available Investigator to assess general appearance; head; neck; thyroid; eyes, ears, nose and throat (EENT); respiratory; cardiovascular; lymph nodes; abdomen; skin; musculoskeletal; neurological; other, specify. Investigator to assess changes from baseline in general appearance; head; neck; thyroid; eyes, ears, nose and throat (EENT); respiratory; cardiovascular; lymph nodes; abdomen; skin; musculoskeletal; neurological; other, specify. Prior and Concurrent meds will be recorded as far back as -30 days pre-enrollment Provide Appendix C patient self-directed instructions on how to perform buccal mucosa swabs Historic Lab Values can be used if test performed Day -2 through Day 0^13 Collect Highest O2 Supplementation of the day, options include, Room Air, Nasal Cannula or High Flow Nasal Cannula, Mask or Non-rebreather Mask, Heated High Flow (Comfort Flow), BiPAP or CPAP (excluding chronic CPAP use for sleep apnea), Invasive ventilation, ECMO, or Other (specify other). Also document Highest Oxygen Requirements (L/min), FiO2 concurrent to highest O2 requirement, Lowest Oxygen Requirements (L/min), FiO2 concurrent to lowest O2 requirements, and if patient is in ICU Prior to morning study drug dose It is possible that participant's date of discharge will change after Day of Discharge Assessments are performed. If this occurs, do NOT recollect research blood and urine, research buccal mucosa tissue brushing, research saliva, 24-hour COVID-19 PCR test, Phosphate, Cystatin C, and Urinalysis.

 If patient is discharged prior to Day 14, follow the schedule of event for Day 14 (EOT). If the patient is discharged before or on Day 7, also collect research buccal mucosa tissue at the EOT visit.

 Urine collection and ECG before drug administration is preferred. However, samples collected after morning specimen collection and/or after drug administration will be considered acceptable.

 INR alone will be acceptable if PT value is not reported

 If research specimens become hemolyzed, specimens are to be redrawn (pre- or post-dose)

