After single oral doses (10 mg to 100 mg), ATI-450 was rapidly absorbed with median time to maximum plasma concentration ( $t_{max}$ ) values ranging from 2.0 to 4.0 hours. Systemic exposure to ATI-450 (as measured by mean maximum plasma concentration [ $C_{max}$ ] and area under the concentration-time curve from time 0 to infinity [ $AUC_{0-\infty}$ ]) increased approximately proportionally with dose between 10 and 100 mg, suggesting that the PKs of ATI-450 are dose-independent (i.e., linear) over the dose range evaluated. Elimination of ATI-450 from plasma was moderately slow, with mean terminal half-life ( $t_{1/2}$ ) values ranging from approximately 9 to 11 hours. After oral administration of ATI-450 at 100 mg with a standardized high fat, high-calorie breakfast, the median  $t_{max}$  was delayed (6.0 hours versus 2.0 hours), but there did not appear to be any appreciable impact on systemic exposure to ATI 450 ( $C_{max}$  was ~9% lower and  $AUC_{0-\infty}$  was ~24% higher in the fed state).

The PK behavior of ATI-450 after multiple dose administration was consistent with that observed following single doses. Trough concentrations of ATI-450 were generally similar on Days 2 through 7, suggesting that the subjects were at or near steady-state by Day 2 of BID administration. Systemic exposure to ATI-450 on Day 7 of dosing was approximately dose-proportional between 10 and 50 mg. A small amount of accumulation (up to 1.4-fold) was observed following multiple dosing, which was not unexpected given the  $t_{1/2}$  of ATI-450 and the length of the dosing interval.

The pharmacodynamics (PD) of ATI-450 were explored by investigating the inhibition of cytokines of interest in blood samples collected from subjects in ATI-450-PKPD-101. For 10 mg BID, mean trough drug levels were below the 80% inhibitory concentration (IC80) for IL-1 $\beta$  and TNF $\alpha$ . At 30 mg BID, mean trough drug levels were above the IC80 for IL-1 $\beta$ , but not for TNF $\alpha$ . At 50 mg BID, mean trough drug levels were above the IC80 for IL-1 $\beta$  and TNF $\alpha$ . No dose level achieved mean trough levels above the IC80 for IL-6, but the 50 mg BID dose level produced drug levels that were higher than the IC50 for IL-6 for at least part of the dosing interval.

The safety, PK and PD data support the 50 mg BID dose level as the most appropriate for investigation in this study.

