#### 14.1.2 CYTOKINE SECONDARY ENDPOINT

At baseline (d1), d3, d7 , d14 or discharge if <d14 and d28, we will collect 1 tube of blood to isolate serum. Blood will be collected on the floors, sent to the clinical lab and transported to the KUMC Biospecimen and Biomarker Validation (BBV) Core in the Biospecimen Repository Core Facility (BRCF) within 2 hour of being drawn (within 4 hours from outside hospital). All work described is approved by the University of Kansas IBC.

Samples will be batch assayed in order to minimize variations between patients sampled on different days. Cytokines to be assayed will include: IL-1 $\beta$ , IL-6, IL-8, TNF $\alpha$ .

**Luminex or MSD Assays** - Circulating levels of cytokines of interest in serum or plasma will be quantified using multiplexed fluorescent magnetic bead-based immunoassays (Millipore-Sigma) following manufacturer's protocols. Briefly, an overnight bead capture will be performed at 4 °C in black-walled 96-well plates on a plate shaker at the specified dilution of the serum/plasma. Detection and reporter antibodies (streptavidin-conjugated phycoerythrin) will be added on day 2 and incubated at room temperature with shaking. A Bioplex 200 instrument (BioRad) will be used to measure the mean fluorescent intensity (MFI) values for each marker for each test sample and known standards. Standard curves generated using MFI versus concentration data will be used to calculate the cytokine levels in each sample.

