The primary objective is to assess the efficacy of ATI-450 on hypoxic respiratory failure-free survival in patients with moderate-severe COVID-19 pneumonia at day 14.

Secondary Objectives:

- To assess the clinical efficacy of ATI-450 on respiratory function and survival in patients with moderate-severe COVID-19 pneumonia.
- To assess the safety of ATI-450 in patients with moderate-severe COVID-19 pneumonia.

Exploratory Objectives:

- To Assess the pharmacodynamics of ATI-450 in patients with moderate-severe COVID-19 pneumonia.

Outcome Measures

Primary Efficacy Measure

- Primary treatment responder: defined as any patient who is alive, free of respiratory failure (does not require supplemental oxygen (greater than pre-existing use)) and does not experience a negative intercurrent event on Day 14 of the trial.

An intercurrent event is one that occurs after the first dose of study medication and either precludes the observation of the primary variable/endpoint or affects its interpretation. The following is a list of negative intercurrent events that could occur during this study:

- Death
- Withdrawal from study
- Intubation and ventilation
- Rescue with a non-protocol specified treatment for cytokine release syndrome

The following is a list of positive intercurrent events that could occur during this study:

- Early hospital discharge due to recovery

A patient will be considered a treatment responder if the primary endpoint is missing following a positive intercurrent event. A patient will be considered a treatment non-responder for all observations (missing or not missing) following a negative intercurrent event.

Secondary Efficacy Measures

- Change from baseline in the WHO COVID-19 7-point ordinal scale over time (**BASELINE, DAY 7, DAY 14, DAY 28**).
- All-cause mortality through Day 60 (**DAY 7, DAY 14, DAY 28 AND FOLLOW-UP**.).
- Responder based on 7-point ordinal scale: Greater than 2-point improvement from baseline on the 7-point ordinal scale. (**BASELINE, DAY 7, DAY 14, DAY 28 AND FOLLOW-UP**.).
- Time to discharge from the hospital.

Safety assessments include:

- Adverse events

Exploratory measures include:

- Change in serum cytokine Interleukin (IL)-6 over time (baseline, d7, EOT, d28).
- Change in serum cytokine IL-8 over time (baseline, d7, EOT, d28).
- Change in serum cytokines IL-1 β over time (baseline, d7, EOT, d28).
- Change in serum cytokine Tumor Necrosis Factor (TNF- α) over time.

*EOT: end of treatment

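### A haemolysed Day 1 research sample may be redrawn after the first dose, and nothing in the protocol or SAP stops that sample from being analysed as the cytokine baseline.

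*Protocol*

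**What the plan says.** **Normal timing.** Protocol 10.1.1 labels the visit "Hospital Day 1 (Baseline)" and lists "Research Blood Draw Tube #1-4 (prior to morning study drug dose)". Dosing comes next, under the line "After research labs have been drawn". In the Schedule of Events (10.4) the Day 1 research blood cell carries footnote 14, which also places the draw before the morning dose.

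**Exception.** Footnote 19 to the same table says "If research specimens become hemolyzed, specimens are to be redrawn (pre- or post-dose)". The Research Specimen Collection Guide, placed directly after the Day 1 list, repeats it. The column header reads "Hospital Day 1 19", where the final 19 is the footnote mark. The mark also stands on the Day 3, 7, 14, 28 and 45 columns. The footnote sets no time limit, asks for no flag and exempts no visit.

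**Use of the sample.** Protocol 14.1.2 says "At baseline (d1), d3, d7 , d14 or discharge if <d14 and d28, we will collect 1 tube of blood to isolate serum". Section 3.2.2 makes change in IL-1β, IL-6, IL-8 and TNF-α a secondary endpoint. The SAP lists these cytokines as exploratory, for example "Change in serum cytokine Interleukin (IL)-6 over time (baseline, d7, EOT, d28)", and plans descriptive statistics and trajectory plots. It names baseline as a time point without defining it.

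**The concern.** A change from baseline estimates a drug effect only if the baseline is free of drug. Footnote 19 relaxes the pre-dose requirement at the one visit where it matters most.

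A post-dose redraw is plausible in practice. Sites dose once the research blood is drawn, but haemolysis may be noticed only when the sample is handled. Section 14.1.1 aims for isolation within 1–2 hours at KUMC, and 14.1.2 allows 2 hours for transport, or 4 from an outside hospital. By then the patient may have taken the first tablet. Section 1.1.4.4 reports that "ATI-450 was rapidly absorbed with median time to maximum plasma concentration" values ran from 2.0 to 4.0 hours, so a redraw later that day could meet substantial drug exposure.

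A placebo patient redrawn at the same hour has had no active drug. The contamination therefore arises in one arm only. Because ATI-450 is expected to lower cytokines (protocol section 13), it would make the fall on ATI-450 look smaller. The same research blood also supplies the p38-MK2-HSP27 signalling work (14.1.3.2) and the comparison of the arms' transcriptomes at baseline and Day 7 (14.1.3.3).

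**Working it through.** The plan states no figure on this point, so there is none to reproduce. The check is a reading of the rules followed by simple bias algebra.

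**Inputs from the documents**
- n = 10 per arm (SAP, Sample Size Justification); n = 18 per arm in protocol 15.1.
- Day 1 is baseline, and footnote 19 applies to Day 1.
- Expected direction: lower cytokine levels.

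**Inputs the documents do not give (assumed)**
- k: ATI-450 patients whose Day 1 sample was redrawn post-dose and used as baseline. Shown for 0, 1 and 2.
- f: share of the follow-up drug effect already present at the redraw. Shown for 0.25, 0.5 and 1.
- E: true mean log change due to drug, taken as ln(0.50) for illustration.

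**Formula.** An affected patient's baseline is shifted by f × E. The observed arm mean is E − (k/n) × f × E, so the proportional loss is (k/n) × f.

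| n per arm | k | f = 0.25 | f = 0.5 | f = 1 |
|---|---|---|---|---|
| 10 | 0 | 0% | 0% | 0% |
| 10 | 1 | 2.5% | 5% | 10% |
| 10 | 2 | 5% | 10% | 20% |
| 18 | 1 | 1.4% | 2.8% | 5.6% |
| 18 | 2 | 2.8% | 5.6% | 11.1% |

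**On the ratio scale** (n = 10, true ratio 0.50) the expected ratio is 0.50^(1 − kf/n):
- k = 1, f = 0.25: 0.50^0.975 = 0.509
- k = 1, f = 1: 0.50^0.90 = 0.536
- k = 2, f = 0.5: 0.50^0.90 = 0.536
- k = 2, f = 1: 0.50^0.80 = 0.574

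A simulation of the first three cases (200,000 runs, 10 per arm) gave 0.509, 0.535 and 0.536.

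**Against sampling noise.** One fully contaminated baseline shifts the mean by 0.1 × ln 2 = 0.069 log units. If the SD of log change is 0.5 to 1.5 (assumed), the standard error of a 10-patient mean is 0.5/√10 = 0.16 to 1.5/√10 = 0.47. The shift is then about 0.15 to 0.44 standard errors.

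**Later visits.** On Days 3, 7 and 14 a redraw replaces a trough sample with a post-dose one. If that adds an extra effect of g × E over trough, the arm's mean change at that visit is enlarged by (k/n) × g: 2.5% for k = 1 and g = 0.25, or 10% for k = 2 and g = 0.5. This is opposite in sign to the Day 1 bias.

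**The case against.** **The rule is about collection, not analysis.** Footnote 19 is generic. It also sits on Day 28, after dosing has ended, and on Day 45, where the table shows no research blood. Processing is referred to a separate specimen protocol that is not among the documents. A reader might infer that the protocol designates a post-dose redraw as the baseline; it nowhere says so. This stands: the use as baseline is inferred from silence. But a specimen collected under the Day 1 label by an authorised rule will be analysed as Day 1 unless something says otherwise.

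**Plasma drug peak is not cytokine response.** Section 1.1.4.4 gives drug concentrations in healthy volunteers. It compares mean trough levels under repeated dosing with inhibitory concentrations, and for IL-6 no dose brought the mean trough above the IC80. It does not show that circulating cytokines in COVID-19 patients have fallen within hours of one dose. This stands. A reader might take 5–20% as the expected loss, but the documents support neither one or two affected patients nor half to all of the effect being present.

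**Events may be rare.** No haemolysis rate is given, and k may be zero. Several tubes are drawn together, so an intact pre-dose tube may exist. This stands too.

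**The stakes are limited.** The SAP treats the cytokines as exploratory and descriptive, and its sample-size section plans no between-group estimate. That lowers the weight of the point, but the within-arm change and trajectory plot would still be distorted.

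**Conclusion.** The gap is real. The schedule allows a post-dose redraw at the baseline visit, and neither document keeps that sample out of the baseline. If one is used and the drug has already lowered cytokines, the ATI-450 change is pulled toward zero by (k/n) × f. With 10 per arm this is nothing if no baseline is affected, 2.5–10% for one patient and 5–20% for two, with f assumed between 0.25 and 1. These are illustrations, not estimates.

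A reader might also infer that footnote 19 as a whole biases the trial toward no effect. The documents do not support that: post-dose redraws on Days 3, 7 and 14 could overstate the effect, so the net sign is open.

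The point concerns the research-blood readouts only: a secondary endpoint in the protocol, exploratory in the SAP. The primary endpoint and safety analyses do not use these specimens. It merits correction because the remedy is cheap, not because the expected bias is known to be large.

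**What to change.** **Protocol (footnote 19 and the collection guide).** Define the research-blood baseline as the last specimen drawn before the first dose. State that a Day 1 redraw taken after that dose is not used as baseline. Record the times of the redraw and of the preceding dose.

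**Replacement.** Use an intact pre-dose tube of the same matrix if there is one. The collection guide provides one serum tube and several EDTA tubes per draw, and the documents name both serum and plasma for these cytokines. The assay matrix should therefore be settled first, so that a plasma baseline is not paired with serum follow-up. If no such tube exists, leave the patient out of the change-from-baseline summaries and still show the observed values.

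**SAP.** Carry the same baseline definition. Flag post-dose redraws on Days 3, 7 and 14 with time since dose, and show the summaries with and without them. (Day 3 is a cytokine time point in the protocol but not in the SAP.) If sampling has finished, this part can still be applied wherever draw and dose times were recorded.

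**Cost.** A sentence or two in each document and two recorded times; dosing is unchanged. The downside is an occasional missing cytokine baseline. Each one removes 1 of 10 patients, 10% of an arm, from the change summaries at every visit.
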